5.1.5 Phone contact (Day 187 +/-1)

Study participants will be contacted by phone at Day 7 to confirm that adverse reactions have subsided. Should this not be the case, an unscheduled visit will be considered as appropriate.

5.1.6 Visit 4 (Day 210 +7)

Study participants will be contacted by phone or mail a few days before Visit 4 to confirm the appointment and be reminded of the need to bring the diary card.

The following activities will be performed during Visit 4:

- The diary card on solicited and unsolicited AEs, SAEs and concomitant medications will be discussed, verified and collected;
- AEs and SAEs will be recorded;
- 29 mL of blood will be collected from all subjects for:
 - Complete blood count;
 - Anti-PT and anti-FHA IgG antibodies by ELISA;
 - Anti-diphtheria and anti-tetanus IgG antibodies by ELISA;
 - Anti-PT neutralizing IgG;
 - Ficoll isolation and freezing of PBMC with preservation and freezing of plasma aliquots;
- The appointment for Visit 5 (Day 365) will be confirmed.

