RATIONALE:	
A significant increase of pertussis incidence is reported in a growing number of countries. This resurgence is considered as resulting from the limited durability of aP-vaccine-induced immunity and is associated with increased mortality in young infants and morbidity at all age groups. As the pertussis immunity acquired through immunization or infection is short-lived, its maintenance or reactivation requires repeat boosting at regular time points. Thus, novel strategies capable of reactivating pertussis immunity are needed.
 
The efficacy of current acellular pertussis vaccines (which contain chemically-detoxified pertussis toxoid (PT)) rapidly wanes, in part because priming and repeat immunization with acellular vaccines induce antibodies specific for the chemically-detoxified PT but unable to efficiently recognize the native PT expressed by B. pertussis.
 
Clinical studies have shown the superior immunogenicity profile of acellular pertussis vaccines including genetically-detoxified PT (rPT) in adults and adolescents previously primed with aP. In particular, we showed in a past Geneva study in teenagers previously primed with aP that rPT/FHA induced a stronger recall response than the current aP-vaccine at one month post-vaccination. However, the difference was less clear one year after vaccination, suggesting that 2 doses may be needed for more sustained immunity.
 
In the present study, we would like to assess whether giving two doses of rPT/FHA at 6 months interval induces stronger immune responses than a single dose.

PRIMARY OBJECTIVE:	
To assess B cell responses to two doses compared to one dose of an acellular pertussis vaccine (Pertagen®) including genetically detoxified pertussis toxin (rPT) when delivered by the intramuscular route to adult volunteers previously primed and boosted with chemically-detoxified PT.
 
 The primary endpoint will be the geometric mean concentration (GMC) of anti-PT neutralizing antibodies assessed 4 weeks (early immunity) and 6 months (sustained immunity) following one or two injections of Pertagen® given at 6 months interval.

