SECONDARY OBJECTIVES:	
 To assess the safety of two doses at 6 months interval of intramuscular immunization with Pertagen® administered to adults as compared to one dose of Pertagen®. To assess the humoral responses elicited by two doses of Pertagen® as compared to a single dose. The following parameters will be assessed at Day 0, Day 28 and Month 6 post first and second vaccination: 
 Geometric mean concentrations (GMCs) of PT, FHA, tetanus and diphtheria-toxoid specific IgG antibodies measured by ELISA Seroresponse rates of PT, FHA, tetanus and diphtheria-toxoid specific IgG antibodies measured by ELISA Seroresponse rates of PT, FHA, tetanus and diphtheria-toxoid specific neutralizing antibodies.

PHASE II/III Pertagen2x VACCINE TRIAL: PROTOCOL v1.2

PROTOCOL SYNOPSIS – PHASE II/III 2 doses rPT-VACCINE TRIAL

EXPLORATORY OBJECTIVES:

- To assess antibody titers to specific neutralizing and non-neutralizing epitopes of PT, by competitive ELISA, following one or two doses of Pertagen®
- To compare antibody avidity following one or two doses of Pertagen®
- To assess the frequency and phenotype of PT-specific memory B cell responses following one or two doses of Pertagen®

STUDY POPULATION: Volunteers, 18-30 years of age

NUMBER OF SUBJECTS: 100 (50 subjects per each vaccine group)

PHASE II/III Pertagen2x VACCINE TRIAL: PROTOCOL v1.2

PROCEDURE AND FOLLOW-UP:

This is a phase II/III, single center, randomized, double-blind controlled vaccine trial in 18 to 30 years old volunteers. It will be performed at the Plateforme de Recherche Clinique de Pédiatrie, Gynécologie et Obstétrique (PGO) of the HUG.

Volunteers who have signed the informed consent and who gave their written assent will be screened clinically for general health status and those who fulfill all exclusion and inclusion criteria will be enrolled into the study.

At Day 0, eligible volunteers will undergo a venous bleed for the determination of baseline values and enter the randomization scheme, being allocated to one of two groups: A (Revaxis® + Pertagen®), B (Pertagen® + Pertagen®) (Tables 1 and 2).

Group A	Revaxis® + Pertagen®	50 subjects
Group B	Pertagen® + Pertagen®	50 subjects

Table 1. Study groups

	Pertagen®	Revaxis®
Active substance		
Tetanus Toxoid (TT)	-	NLT 20IU
Diphtheria Toxoid (DT)	-	NLT 2.0 IU
Pertussis Toxoid (PT)	5 µg ^a	-
Filamentous Hemagglutinin (FHA)	5 µg	-
Pertactin (PRN)	-	-
Fimbriae type 2/3	-	-

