Inactivated polio viruses type 1-2-3	-	40U (type 1), 8U (type 2), 32U (type 3)
Adjuvants		
Aluminum Hydroxide	0.3 mg/dose	0.35mg/dose
Volume for Injection	q.s. to 0.5 mL	q.s. to 0.5 mL
a: Recombinant Pertussis Toxin (rPT)		

Table 2. Composition of each dose of 0.5mL presented in pre-filled syringe

Visit 1: Randomized participants will receive one dose of Revaxis® (Group A) or one dose of Pertagen® (Group B) by intramuscular injection in the deltoid. All volunteers will be observed at the Plateforme de Recherche Clinique PGO for 30 minutes after immunization.

Diary cards will be distributed to study volunteers to record post-immunization local and systemic reactions avec adverse events. Volunteers will complete daily diaries for 7 days after immunization.

All volunteers will be followed for 28 days after immunization and all adverse events will be collected and monitored for 28 days after vaccination.

Visit 2: At Day 28, a second visit will take place for safety evaluation, blood draw and revision of diary cards. Investigators will reconcile and transcribe the Diary Card information in the CRF.

Visit 3: At 6 months, a third visit will take place for the second vaccination. Randomized participants will all receive one dose of Pertagen® (Groups A and B) by intramuscular injection in the deltoid. All volunteers will be observed at the Plateforme de Recherche Clinique PGO for 30 minutes after immunization.

Diary Cards will be distributed to study volunteers to record post-immunization local and systemic reactions and adverse events. Volunteers will complete daily diaries for 7 days after immunization.

All volunteers will be followed for 28 days after immunization and all adverse events will be collected and monitored for 28 days after vaccination.

Visit 4: At Day 28 post second immunization, a 4th visit will take place for safety evaluation, blood draw, and revision of diary cards. Investigators will reconcile and transcribe the Diary Card information in the CRF.

Visit 5: A final visit will take place at 6 months post-second immunization (blood draw).

At this visit, Group 2 participants will be offered one dose of Revaxis® if needed for their protection (last dose of tetanus-containing vaccine \geq 10 years).

Blood draws performed on Day 0 (Baseline), Day 28, and Month 6 following each vaccination will be used to evaluate early and sustained vaccine responses.

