5.1.3 Visit 2 (Day 28 +7)

Study participants will be contacted by phone or mail a few days before Visit 2 to confirm the appointment and be reminded of the need to bring the diary card.

The following activities will be performed during Visit 2:

- The diary card on solicited and unsolicited AEs, SAEs and concomitant medications will be discussed, verified and collected;
- AEs and SAEs will be recorded;
- 29 mL of blood will be collected from all subjects for:
 - Complete blood count;
 - Anti-PT and anti-FHA IgG antibodies by ELISA;
 - Anti-diphtheria and anti-tetanus IgG antibodies by ELISA;
 - Anti-PT neutralizing IgG;
 - Ficoll isolation and freezing of PBMC with preservation and freezing of plasma aliquots;
- The appointment for Visit 3 (Day 180) will be confirmed.

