5.1.4 Visit 3 (Day 180 +/- 30)

Study participants will be contacted by phone or mail a few days before Visit 3 to confirm the appointment.

The following activities will be performed during Visit 3:

- 29 mL of blood will be collected from all subjects for:
 - Complete blood count;
 - Anti-PT and anti-FHA IgG antibodies by ELISA;
 - Anti-diphtheria and anti-tetanus IgG antibodies by ELISA;
 - Anti-PT neutralizing IgG;
 - Ficoll isolation and freezing of PBMCs with preservation and freezing of plasma aliquots;
- The treatment will be administered in a double-blind manner. All subjects will remain under close observation at the clinical trial unit (CTU) for 30 minutes;
- A diary card for recording daily symptoms will be explained and distributed to all subjects;

- Subject will be given an emergency card with a phone number to call in case of questions or upon occurrence of any AE;
- The appointment for Visit 4 (Day 210) will be confirmed.

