8.3 Immunogenicity analyses

The primary immunogenicity endpoint will assess the immune response to two doses of Pertagen®, as compared to one dose, by measuring the Day 28 geometric mean concentration (GMC) of neutralizing antibodies to PT after immunization.

The other immunogenicity end-points are listed in Section 2.2 of this protocol.

The following descriptive statistics will be provided for each variable: number of subjects, percentages, mean, geometric mean, standard deviation, median, minimum, maximum, and range.

Immunogenicity endpoints and confidence bounds will be calculated for each group and compared (using Chi-square or Fisher's exact test for binary endpoints, and Wilcoxon-Mann-Whitney's test or Kruskal-Wallis test for quantitative endpoints). All tests will be two-sided.

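### Visit 4 is set at 28 days after dose 2 in the synopsis but at study Day 210 +7 in section 5.1, although dose 2 may fall anywhere from Day 150 to Day 210

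*Combined protocol and SAP*

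**What the plan says.** The outcome text counts time from injection. The primary objective in the synopsis has neutralizing anti-PT antibody "assessed 4 weeks (early immunity) and 6 months (sustained immunity) following one or two injections of Pertagen". The secondary outcomes, in the synopsis and in section 2.2.2, follow the same pattern: "The following parameters will be assessed at Day 0, Day 28 and Month 6 post first and second vaccination". Section 8.3 defines the primary endpoint "by measuring the Day 28 geometric mean concentration (GMC) of neutralizing antibodies to PT after immunization". The procedure part of the synopsis applies this to the visit itself, "Visit 4: At Day 28 post second immunization, a 4th visit will take place", and bases the primary analysis on Visits 4 and 5.

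The visit schedule counts from enrolment. The second injection is given at Visit 3, headed "5.1.4 Visit 3 (Day 180 +/- 30", and the next sample is headed "5.1.6 Visit 4 (Day 210 +7". The Visit 3 checklist, completed when the true injection date is known, ends with "The appointment for Visit 4 (Day 210) will be confirmed". Sections 4.4 and 5.3 also call this visit Day 210. Section 5.1 gives each visit its own time point and window, and allows the Principal Investigator to permit departures in exceptional situations.

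The corresponding visit after dose 1 is headed "5.1.3 Visit 2 (Day 28 +7". Since dose 1 is given on Day 0, study day and days since injection are the same there.

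**The concern.** Both groups receive Pertagen at Visit 3, so Visit 4 is the early sample on which one dose is compared with two. The endpoint has meaning only as a time since that injection. Under section 5.1 the injection date can move by 30 days either way, while the sampling window stays on the calendar of study days. A sample could then be fully compliant with section 5.1 and be analysed as Day 28, yet have been drawn at a clearly different interval from dose 2. The documents also give no rule for restricting or adjusting the analysis by actual interval.

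Safety text is touched as well. Section 4.4 treats the 28 days of adverse event collection after each vaccination as the period up to Visit 4. That cannot hold in window for the later permitted injection dates.

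**Working it through.** **Inputs**
- Dose 2 (Visit 3): Day 180 +/- 30, so Day 150 to 210, which is 210 − 150 + 1 = 61 permitted days (section 5.1.4). The nominal day is 180 (section 4.2.3).
- Visit 4: Day 210 +7, so Day 210 to 217 (section 5.1.6).
- Target: 28 days after the second injection (synopsis). The synopsis gives no window, so the Visit 2 window, 28 to 35 days (section 5.1.3), serves as the benchmark.

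Let *s* be the study day of dose 2. An in-window Visit 4 then falls between 210 − *s* and 217 − *s* days after dose 2.

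**1. The plan's own figure at the nominal date.** With *s* = 180, 28 days later is 180 + 28 = Day 208, before the window opens on Day 210. The in-window interval is 210 − 180 = 30 to 217 − 180 = 37 days. The stated Day 28 is not reproduced, though the miss is small.

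**2. Exactly 28 days.** This needs 210 − *s* ≤ 28 ≤ 217 − *s*, so *s* = 182 to 189: 8 of 61 days.

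**3. Any date at 28 to 35 days.** This needs 210 − *s* ≤ 35 and 217 − *s* ≥ 28, so *s* = 175 to 189: 15 of 61 days.

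**4. The other 46 days.**

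| Dose 2 on | Permitted days | In-window Visit 4 closest to the benchmark |
|---|---|---|
| Day 150–174 | 25 | 60 down to 36 days after dose 2 (210 − *s*) |
| Day 175–189 | 15 | 28–35 days reachable |
| Day 190–210 | 21 | 27 down to 7 days after dose 2 (217 − *s*) |

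**5. Adverse event period.** For *s* ≥ 190, *s* + 28 ≥ 218, which is after Day 217. On those 21 days the Visit 4 window closes before the 28-day period in sections 4.4 and 7.7 is complete.

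**6. Phone contact.** Section 5.1.5 is headed Day 187 +/-1 (Day 186 to 188), but its body says Day 7. Seven days after dose 2 falls on Day 186 to 188 only for *s* = 179 to 181.

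**7. Counted from the injection.** With Visit 4 at *s* + 28 to *s* + 35, every in-window sample is at 28 to 35 days. On the study calendar that is Day 178–185 for *s* = 150, Day 208–215 for *s* = 180 and Day 238–245 for *s* = 210.

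The counts in steps 2 to 5 are of permitted injection days, not of participants. The documents give neither the spread of Visit 3 dates nor the booking practice, so the share of samples affected is unknown.

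**The case against.** The best defence is that Day 210 is a nominal label. The synopsis ties Visit 4 to the second immunization, section 4.4 links it to 28 days after vaccination, and section 5.1.5 carries a study-day heading over a body that counts from dose 2. Section 4.2.3 simply places dose 2 at Day 180. On that reading staff would book Visit 4 about four weeks after whatever date Visit 3 took place, and the difference at the nominal date is only 30 versus 28 days. The Principal Investigator may also allow off-window visits, with immunogenicity evaluation named as one purpose.

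Much of this stands. The protocol does contain an anchor to dose 2, so the fault is a failure to carry it into section 5.1, and site staff may well follow the intended meaning. But section 5.1 does not call its days nominal, and the Visit 3 checklist books by study day. Discretion kept for exceptional situations is a weak remedy when 46 of the 61 permitted dose 2 days would need it to reach 28 to 35 days.

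The flow chart is not shown and the schedule table is broken in the text available. An anchor there cannot be excluded.

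**Conclusion.** The inconsistency is real and should be fixed. The synopsis and section 5.1 give different times for a primary-analysis sample. Taken literally, section 5.1 allows 28 to 35 days after dose 2 on only 15 of 61 permitted injection days and exactly 28 days on 8; on 21 it closes the visit before adverse event collection is complete. This rests on reading section 5.1 as fixed study days and on borrowing the Visit 2 window as the benchmark.

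A reader might infer more than the documents support:
- **That samples will be taken 0 to 67 days after dose 2.** The windows alone permit this (210 − 210 = 0; 217 − 150 = 67). The low end, however, conflicts with the 7-day diary collected at Visit 4, the phone contact a week after dose 2 and the 28-day adverse event follow-up. It is not a workable schedule.
- **That the group comparison is biased.** Both arms are randomized, blinded and share the same windows. The harm is added timing variability and a blurred time point.
- **That power is lost by a known amount.** The documents give no antibody kinetics after dose 2, so no effect on variance or power can be computed. Section 8.1 also declares p-values exploratory.
- **That Visit 5 has the same contradiction.** Its window, Day 335 to 395, is wide enough. Taking 6 months as 180 to 185 days, *s* + 180 is in window for *s* = 155 to 210 (56 of 61 days) and *s* + 185 for all 61.

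**What to change.** In sections 5.1.6, 4.4 and 5.3 and in the schedule table, define the whole of Visit 4, blood sampling and safety review together, as Day 28 +7 counted from the actual date of the second injection. This matches the synopsis and Visit 2. Change the appointment line in the Visit 3 checklist (section 5.1.4) to agree. With the whole visit moved, the statement in section 4.4 that the 28-day adverse event period runs to Visit 4 can hold for every permitted injection date. The heading and body of section 5.1.5 must also be reconciled with each other.

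The cost is wording only. No visits, blood volume or participants are added, the injection schedule is unchanged and Visit 5 stays as it is. The small downside is that Visit 4 falls on a study day that varies with the date of dose 2, from Day 178–185 to Day 238–245 at the extremes, so it must be booked individually at Visit 3.

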5.1.7 Visit 5 (Day 365 +/- 30)

Study participants will be contacted by phone or mail a few days before Visit 4 to confirm the appointment.

The following activities will be performed during the final Visit:

- 29 mL of blood will be collected from all subjects for:
 - Complete blood count;
 - Anti-PT and anti-FHA IgG antibodies by ELISA;
 - Anti-diphtheria and anti-tetanus IgG antibodies by ELISA;
 - Anti-PT neutralizing IgG;
 - Ficoll isolation and freezing of PBMC with preservation and freezing of plasma aliquots;
- Participants will be offered one dose of Revaxis® if needed for their protection.

5.2 Unscheduled visits

Subjects may contact the Clinical Investigator at any time for an unscheduled phone or on-site visit should they experience clinical symptoms or signs following treatment. At all unscheduled visits the following minimum will be performed:

- Questions concerning the history of the present illness as well as the subject's general health;
- Medically attended AEs and any possible SAEs will be recorded;
- Any concomitant medication will be noted (any other vaccination is forbidden during the study duration).

After eliciting the history of the present illness and performing any corresponding exams or laboratory tests, the Clinical Investigator will decide on the best course of treatment according to standard medical practice.

5.3 Study assessments

For each study subject, the blood volume taken per visit lies in the range of 29mL for immunologic assays. Blood will be taken on Day 0 and Day 180 (Baseline/vaccination days), as well as Day 28, Day 210 and Day 365 (to assess the response to immunization).

5.3.1 Safety tests

Safety tests will include:

- Vital signs evaluation: heart and respiratory rates, systolic and diastolic blood pressure and axillary body temperature at baseline;
- Local and systemic reactivity assessed 30 minutes after vaccination at the Plateforme de Recherche Clinique PGO;
- Local and systemic reactivity assessed through diary cards, during 7 days after immunization;
- Other adverse events or serious adverse events during 28 days after immunization;
- Study Participants will be able to contact us at any time in case of any adverse event.

5.3.2 Immunogenicity tests

The immunogenicity of both Pertagen® + Pertagen® and Revaxis® + Pertagen® will be assessed in all subjects by ELISA-based detection of antigen-specific human IgG in serum samples. Sera will be assessed by the pertussis toxin neutralization assays to characterize the functionality of anti-PT antibodies.

PBMCs will be frozen on site for subsequent analyses of the frequency and phenotype of specific B or T-cell responses before/after vaccination.

6 STUDY DISCONTINUATION

The study in its entirety may be discontinued prematurely with reasonable justification by the Principal Investigator (PI), Sponsor, Swissmedic or the Ethics Committee with oversight responsibilities at any time (see below), and/or individual subjects may terminate their participation prematurely, or have their participation be terminated by the Investigator.

6.1 Study termination

The PI, Sponsor, Swissmedic or the Ethics Committee with oversight responsibilities for the trial may terminate the trial at any time with reasonable justification. In the case of study termination, investigators will be informed of the procedures to be followed to ensure adequate consideration is given to the subject's safety.

The Investigator will be responsible for informing the Sponsor of the trial's termination within 24 hours, and, in accordance with art. 37 Oclin, the Sponsor notifies Swissmedic within 7 calendar days.

6.2 Study withdrawal

In accordance with the principles of the current revision of the Declaration of Helsinki, a volunteer has the right to withdraw from the study at any time and for any reason, and is not obliged to give his or her reason(s) for doing so. The Investigator may withdraw the volunteer at any time in the interests of the volunteer's health and well-being. In addition the volunteer may withdraw/be withdrawn for any of the following reasons:

- Ineligibility (either arising during the study or retrospectively, having been overlooked at screening); if the ineligibility is discovered after study application, the participant will be withdrawn from the study only in the event that the factor leading to ineligibility could directly jeopardize the health of the participant;
- Significant protocol deviation: failure to obtain informed consent prior to any study-specific test or procedure, or failure to follow protocol procedures that specifically relate to the primary safety and/or immunogenicity endpoints of the study;
- Volunteer non-compliance with study requirements;
- An AE, which requires discontinuation of the study involvement or results in inability to continue to comply with study procedures.

The reason for withdrawal will be recorded in the CRF. If withdrawal is due to an AE, appropriate follow-up visits or medical care will be arranged, with the agreement of the volunteer, until the AE has resolved, stabilized or a non-trial related causality has been assigned. Any volunteer who is withdrawn from the study may be replaced (see 6.3 Procedures for handling subjects with premature study discontinuation), if that is possible within the specified time frame (i.e., before the termination of study recruitment). The DSMB may recommend withdrawal of volunteers.

Further stopping rules

The Sponsor is entitled to terminate the study at any time for the following reasons:

- Negative criticism on the execution of the study. Upon signals that investigator did not react properly to complaints expressed by participants, violate the study protocol or perform unacceptably otherwise, the investigator(s) may be 'frozen' until further notice, to review the case;
- New data on the safety of the product under study that become known during the study that makes further use of the product undesirable, even in a controlled situation;
- Early results from the study that indicates failure or unsafety of the product under study;
- When investigators come into a situation that impedes the further progress of the study, the study may be discontinued if the investigator cannot be replaced or no other solution can be found.

